- Of the up to 22 questions indicated for the Screening/Enrollment or Baseline interviews, a module of 9 will not be asked again during the study either because the responses will not change, or because they are intended only to indicate status at the outset of the study (i.e., mother DOB, race/ethnicity, US born, parity, and prior WIC receipt,
- Similarly, maternal employment during pregnancy is asked only once, at 1 month.

 Of note: the baseline interview could be the Prenatal, the 1-month, or the 3-month interview, depending on when the mother was recruited. Furthermore, the screening/enrollment interview takes place on site and is not part of the prenatal, 1-month, or 3-month interviews.

Table 3-2 Example of modular nature of variables

Variables by Domain	Enrollment/ Screening	Baseline a	Prenatal	1 month	3 months	5 months	7 months	9 months	11 months	13 months	15 months	18 months	24 months
Socio-demographics and Background Characteristics													
Maternal birth date	✓												
Maternal ethnicity	✓												
Maternal race	✓												
US or foreign born		✓											
Marital status		✓								✓			
Parity		✓											
Interpregnancy interval/interpartum period		✓											
Number of children in household		✓											
Due date, if enrolled prenatally	✓												
Infant DOB b	[✓]			[✓]									
Single or multiple birth b	[✓]			[✓]									
Child name b	[✓]			[✓]									
Child sex b	[✓]			[✓]									
Child ethnicity b	[✓]			[✓]									
Child race b	[✓]			[✓]									
Respondent still caregiver/new caregiver information				✓	✓	✓	✓	✓	✓	✓	✓	✓	✓
New pregnancy/due date							✓			✓		✓	
Household size	✓						✓			✓			✓
Household income	✓						✓			✓			✓
Presence of infant's father		✓								✓			
Receipt of public assistance		✓								✓			✓
Brief household food insecurity							✓			✓			
6-item food insecurity													✓

Table 3-2 Example of modular nature of variables (continued)

Variables by Domain	Enrollment/ Screening	Baseline a	Prenatal	1 month	3 months	5 months	7 months	9 months	11 months	13 months	15 months	18 months	24 months
Socio-demographics and Background Characteristics													
Use of emergency food sources													✓
Prior WIC receipt		✓											
Number of prior children on WIC		✓											
Duration of prior WIC receipt (mother and/or children total years)		✓											

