### ***WIC Program Variables***

A key variable of interest in assessing infant feeding practices is the mother's experience with the WIC program. There is variation in participants' experiences with WIC because there are differences in: (1) the services and education provided at the local clinic, (2) the State policies and supplies provided (3) the training and attitudes of the local WIC clinic staff, and (4) the time spent in the program. Westat proposes to improve the measure of participants' WIC program experience and capture this variation by developing a series of composite measures. We propose five composite

measures for capturing program variation and identify the expected contributing factors to each measure as follows:

- **Variation in education offered** measured by the number of education contacts offered, educational topics offered, delivery method, training of the staff, knowledge and attitudes of the staff. (In addition to this program-offering composite, we will have information on the educational programs the individual attended which can be used as a separate covariate).
- **Variation in breastfeeding peer counseling** measured by the ratio of counselors to participants, education and training of the staff, and knowledge and attitudes of the staff; and
- **Variation in the provision and support for breast pumps** measured by types of pumps available, policies on issuance, support education provided, and knowledge and attitudes of the staff regarding pumps
- **Variation in the food packages** measured by package choice substitutions available based on the State plan and attitudes of the staff regarding the importance of the food packages, substitutes, and alternative diets.
- **Variation in time in WIC** measured by number of days of current participation, number of years of participation associated with previous children, joined pre-natal or post-partum.

We will use these composite variables to capture the cross-sectional variation in WIC program experience, or “dosage” of WIC exposure, among program participants.

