It should be noted that ultimately the variation in service delivery we observe between sites will determine which factors to include in our composite measures as well as whether the final measures are effective in capturing meaningful program variation that can be related to policies. Therefore, to some extent this work will be exploratory and we will assess alternative composites. For example, if we find the quality of sites’ educational programs vary by phase we will consider having separate composites for newborn feeding, infant feeding transition, and toddler feeding. In contrast, if sites that deliver effective newborn feeding education, almost always also deliver strong infant feeding transition and toddler feeding programs, a single education composite will suffice.

---

The WIC program variables will be composite measures. A composite measure is a combined metric that incorporates multiple individual measures to provide a single score. It is used as a way to measure concepts that are too complex to be measured simply with one item. Composite measures are also a data reduction technique used to avoid having many highly correlated variables in the same analyses which creates statistical challenges. The five WIC program variables will be composite measures of the component variables listed in the Research Plan and are intended to capture different aspects of how the program is being delivered and experienced. For each of the five composite measures, we will develop weights for the component variables and combine them into a single score (index variable). A simple approach for doing this is to take a straight average of all the component variables but this approach would not address the differing importance of the component items or their correlation with each other. We propose to use factor analysis (a statistical technique) to determine the relative weights to use in the creating the composite measure.

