Introduction of other foods	
 
■ Time until cereal
 
■ Time until fruits
 
■ Time until vegetables
 
■ Time until meats
 
	
 
■ Survival analysis
 
	
 
■ Socio-demographics: Age, race/ethnicity, born in US, household size, income, poverty level, use of child care, returned to work or school, education
 
■ Feeding practices: current use of formula
 
■ Attitudes, beliefs and knowledge: Belief formula provided from WIC is insufficient, parental assessment of baby's weight
 
■ Prenatal experience and advice: Receipt of breastfeeding information from non-WIC sources
 

Table 7-3. Proposed model specifications (continued)

Model	Dependent variable	Estimation methods	Minimum covariates to explore
			
 
■ WIC program experience: Education, time in WIC
 
■ Return to work/school: Returned to work/school within 2 months
 

Weight	
 
■ Child's weight/length (6, 12, and 24 months)
 
	
 
■ OLS
 
■ Quantile regression
 
	
 
■ Socio-demographics: Gender, race/ethnicity, income, born in US
 
■ Maternal/family health: Maternal BMI, paternal obesity, maternal diabetes, smoking during pregnancy, household food security (24 months only), maternal fruit and vegetable dietary intake (24 months only)
 
■ WIC program experience: Education, food package, time in WIC (and peer counseling for 6 month weight/length)
 
■ Child's health and physical activity: birth weight, premature, rapid early weight gain, physical activity indoors, physical outdoors (for 24 month measure) current sleep duration
 
■ Basic dietary intake: Breastfeeding duration, current intake of sweetened beverages
 
■ Feeding practices: Clean plate policy, track eating, careful not to feed too much
 

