Growth	
 
■ Repeated measures of child's weight/length
 
	
 
■ Growth model
 
	
 
■ Socio-demographics: Gender, race/ethnicity, income Maternal/family health: Maternal BMI, paternal obesity, maternal diabetes, smoking during pregnancy
 
■ WIC program experience: Education, food package, time in WIC
 
■ Child's health and physical activity: Birth weight, premature
 
■ Basic dietary intake: Breastfeeding duration
 

We will estimate several variants of the breastfeeding decision model. First, we will use two alternatives for the dependent variable: initiating breastfeeding and breastfeeding at hospital discharge. Similarly, we will explore using dichotomous measures (yes, no) for these variables as well using categorical measures that capture mixing breastfeeding and formula feeding from the start. Additionally, we will have mother's prenatal attitudes collected prior to delivery (rather than retrospectively) and can also explore how their breastfeeding intentions for initiation and duration affect actual initiation and exclusivity. Finally, for this model we will explore the viability of using a summary index to capture the mother's attitudes, beliefs, and knowledge on breastfeeding and her hospital experience in place of the individual covariates in these groups.

Our estimates of the formula supplementation model and time until the introduction of other foods models will closely parallel the past work with few extensions. In estimating the formula supplementation model we will explore how breastfeeding intentions regarding duration (which is typically not collected) affect the time until formula supplementation. The covariates we will examine for predicting the time until breastfeeding cessation and the introduction of cereals, fruits, and vegetables will parallel those used in the IFPS-1 study.

For the new weight model, we will run separate models estimating weight/length for the children at 6, 12, and 24 months. In addition to including direct measures of toddler feeding practices (such as family has a clean plate policy), we will explore the viability of using summary measures of a range of toddler feeding practices to predict weight outcomes.

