Finally, in all these models we will capture the cross-sectional variation in the WIC program experience through the inclusion of WIC program composite measures which will be an enhancement over past studies. For breastfeeding initiation and duration decisions, we expect that the variation in educational programs, peer counseling and the provision and support for breast pumps will be factors affecting individuals' decision. For infant feeding transitions and toddler weight outcomes, we expect that variation in education and the food packages will be important factors. For all of these decisions and outcomes, we expect that the time the mother has spent in WIC will be an important predictor.

This page left intentionally blank

Table 8-1 provides a summary of our proposed analytical report schedule and the content of each report. There are a few topic areas that draw solely from data collected during the first few interviews and these analyses can be completed prior to finishing all the data collection. Analyses of prenatal views, the study design and sample, breastfeeding decisions, hospital practices and neonatal circumstances, and breastfeeding problems can be completed prior to conducting the 13 months interview. Additionally, the analyses on formula supplementation, breastfeeding and formula feeding practice, and the continuation and cessation of breastfeeding can be completed using data through the month 13 interview. The analyses of all the other topic areas at least partially depend on data collected from later interviews. Therefore, as our report schedule shows, there are some topics for which we will provide preliminary analysis based on the currently available data and then update these analyses in final infant and final infant and toddler reports. Please note, that while we are contracted to deliver 4 interim reports on the toddler interviews, since FNS eliminated the 21 month interview, we have only 3 data collection interviews. We have some suggestions for the content of the 4th report we would like to discuss with FNS.

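### Time in WIC counts years on WIC with earlier children, but the food-introduction, Weight and Growth models list no birth-order covariate, so part of any birth-order difference can appear as a time-in-WIC effect

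*Combined protocol and SAP*

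**What the plan says.** Section 7.2 (WIC Program Variables) defines five composite measures of WIC experience. The time-in-WIC composite combines days of current participation with "number of years of participation associated with previous children, joined pre-natal or post-partum". Footnote 17 leaves the weighting to the data: "We propose to use factor analysis (a statistical technique) to determine the relative weights to use in the creating the composite measure".

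Section 7.5, in the text after Table 7-3, says that "in all these models we will capture the cross-sectional variation in the WIC program experience through the inclusion of WIC program composite measures". It adds that, for all these decisions and outcomes, "we expect that the time the mother has spent in WIC will be an important predictor".

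In Table 7-3 the Weight model's background covariates are "Socio-demographics: Gender, race/ethnicity, income, born in US". The Growth model lists gender, race/ethnicity and income, and its programme line is "WIC program experience: Education, food package, time in WIC". The food-introduction model lists maternal age and household size but no birth-order term. The three breastfeeding models do list first-born status.

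Elsewhere the plan treats birth order as relevant. Section 7.2 (Comparison Groups and Covariates) puts it among the core comparison groups, and Section 7.5 lists parity as a key subgroup. Table 3-2 collects parity once, at baseline, along with a row on earlier WIC use that begins "Duration of prior WIC receipt (mother and/or children total years".

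**The concern.** The prior-children component is zero for every first birth and can be positive only for later births. The composite is therefore likely to be correlated with birth order for reasons unrelated to what WIC does for the index child. A model that contains the composite but no birth-order term can attribute to WIC a difference that belongs to being a first or a later child.

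The interpretation raises the stakes. Section 7.3 classes the model estimations as causal analyses, and Section 7.2 describes the composites as capturing the dose of WIC exposure. A reader of the final report would naturally take a non-zero time-in-WIC coefficient in the Weight or Growth model as a programme effect on child weight. Section 7.5 provides for trying alternative proxies when a variable proves insignificant, so a coefficient made significant by birth order would not trigger that check.

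**Working it through.** **1. What each Table 7-3 model lists**

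| Model | Time in WIC | Birth-order term | Possible proxy |
|---|---|---|---|
| Breastfeeding decision | yes | first-born | breastfed earlier children |
| Formula supplementation | yes | first-born | – |
| Breastfeeding cessation | yes | first-born | – |
| Food introduction | yes | none | household size, maternal age |
| Weight | yes | none | no direct one |
| Growth | yes | none | no direct one |

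**2. Which variable is zero.** The zero for first births belongs to the Section 7.2 component, years tied to previous children. The Table 3-2 item counts total years for the mother and/or children, so it is not identical to that component. The other two components, days of current participation and prenatal or postpartum entry, are not zero by construction.

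**3. Size for the composite.** The plan gives no figure to reproduce, so this is an illustration. With no WIC effect and no other covariates, the spurious coefficient per SD of score is

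b = d × r × √(p(1 − p)),

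where d is the birth-order difference in outcome SDs, r the correlation of the score with being later-born, and p the share of first births.

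Assumptions, none of them from the documents:
- p is 30% to 50%.
- 50% to 80% of mothers with earlier children had WIC years with them. Those mothers have 1.6 earlier children on average, with two WIC years per child.
- 80% enrol prenatally.
- The prior-years component has weight 0.2 to 0.6, and the rest is split equally between the other two components.
- d = 0.2.

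A simulation of 200,000 records for each of 18 combinations gave r from 0.10 to 0.50 and b from 0.008 to 0.053. The formula agrees at both ends:
- p = 0.3, r = 0.10: 0.2 × 0.10 × 0.458 = 0.009 (simulated 0.008).
- p = 0.5, r = 0.50: 0.2 × 0.50 × 0.5 = 0.050 (simulated 0.053).

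The simulation error is about 1/√200,000 = 0.002.

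**4. False-positive rate.** SE = √(deff/n), with assumed n of 1,500 to 2,500 and design effect of 1 to 2. The rate is 1 − Φ(1.96 − b/SE) + Φ(−1.96 − b/SE).
- Lowest: b = 0.008, n = 1,500, deff = 2. SE = 0.0365, b/SE = 0.22, rate 0.06.
- Highest: b = 0.053, n = 2,500, deff = 1. SE = 0.020, b/SE = 2.65, rate 0.75.

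The component weight is the main driver. With p = 0.4, 80% prior use, n = 2,500 and deff = 1, the rate is 0.14, 0.28 and 0.63 at weights 0.2, 0.33 and 0.6.

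**5. Adding covariates.** Household size (simulated as two, plus earlier children, plus others averaging one) lowers b to between 0.004 and 0.034, removing about 36% to 55% of it. A first-born indicator brings b to between −0.005 and 0.003, which is zero within simulation error. The simulation imposes a simple first-versus-later step, so a yes/no term is sufficient by design.

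**6. Cost in precision.** Suppose that 60% of mothers have earlier children and that their prior WIC years have mean μ and SD s. Then cov = 0.24μ, var = 0.6(s² + μ²) − (0.6μ)², and the correlation of prior years with being later-born is cov/√(0.24 × var):
- μ = 3, s = 2: 0.72/√(0.24 × 4.56) = 0.69.
- μ = 4, s = 3: 0.96/√(0.24 × 9.24) = 0.64.
- μ = 5, s = 3: 1.20/√(0.24 × 11.4) = 0.73.

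The standard error of a separate prior-years term, once birth order is in the model, grows by 1/√(1 − r²). From the unrounded correlations that is 1.31 to 1.45.

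**The case against.** The best defence is that Table 7-3 is not a closed list. Its covariate column is headed as a minimum set to explore, Section 7.2 speaks of the core socio-demographic variables as covariates in general, and it calls the composite work partly exploratory. This stands to the extent that the gap is an inconsistency between Section 7.2 and three rows of Table 7-3, not a decision to exclude parity. It does not close the gap: Section 7.5 calls the table the detailed specification, and nothing commits the analysts to adding birth order to those rows.

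A reader might also go too far the other way and treat prior WIC years as if they were the whole score. With the three settings in step 6, n = 2,000 and a design effect of 1.5 (SE 0.027), a 0.2 SD birth-order difference would then give a spurious coefficient of 0.063 to 0.071 and a false-positive rate of 64% to 74%. The documents do not support those figures as properties of the planned analysis. The component is one of three, its weight is not yet set, and the calculation ignores every listed covariate. Household size partly covers the food-introduction model, and the Weight model's birth weight, prematurity, early weight gain and breastfeeding duration may carry some of a birth-order difference.

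Two further points stand. The first-born term already deals with the main contrast in the three breastfeeding models. And the first four models start from the IFPS-1 covariates for comparability, which is a reason not to replace terms there.

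**Conclusion.** The point holds as an omission with a real but unquantified consequence. Table 7-3 as written leaves a confounding path open between the time-in-WIC composite and birth order. The path is widest in Weight and Growth, which have no direct proxy, and narrower in food introduction.

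Whether it matters depends on two things that the documents do not give: the weight that factor analysis assigns to the prior-children component, and whether the outcome differs by birth order once the listed covariates are in. Under the assumptions shown, the effect runs from negligible (0.01 SD per SD of score, 6% false positives) to serious (0.05 SD, 75%).

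It would be wrong to infer that a birth-order difference will be reported as a WIC effect, or that all of it would load on the score. Only part of a difference can, and only if one exists. This is a cheap improvement.

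**What to change.** 1. In Table 7-3, list first-born or parity as a fixed covariate in the Weight, Growth and food-introduction models. For food introduction, keep the run with the IFPS-1 covariates as the comparison version and add birth order in the extended version. Weight and Growth are new models, so no comparability is lost there.
2. In the extended models, enter WIC years with earlier children separately from exposure for the index child, and interpret that coefficient as a contrast among mothers with earlier children.
3. Leave the first-born term in the three breastfeeding models as it is.

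The cost is wording and a few degrees of freedom, since parity and prior WIC receipt are already collected at baseline. The real price is precision: under the assumed correlations of 0.64 to 0.73, the interval for the separate prior-years coefficient is roughly 30% to 45% wider than without a birth-order term.

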Educational attainment		✓											✓
Current educational status					✓		✓			✓		✓	✓
Employment during pregnancy				✓									
Current employment status					✓		✓			✓		✓	✓
Age of child when mother began school or work c					[✓]		[✓]			[✓]		[✓]	[✓]
Continuation/discontinuation of WIC participation				✓	✓	✓	✓	✓	✓	✓	✓	✓	✓
Location of WIC service receipt				✓	✓	✓	✓	✓	✓	✓	✓	✓	✓
If WIC discontinued, age of child when WIC discontinued				✓	✓	✓	✓	✓	✓	✓	✓	✓	✓
If WIC discontinued, reasons for leaving WIC				✓	✓	✓	✓	✓	✓	✓	✓	✓	✓

a Questions will be asked at the first interview (could be prenatal, 1 month, or 3 month)

b Asked at enrollment if enrolled in study after child's birth; asked at 1 month if enrolled in study prenatally. The bracketed checks indicate times when this could be asked conditional upon time of enrollment.

c Asked the first time postnatally that the mother reports that she is currently working for pay. The bracketed checks indicate times when this could be asked.

- Some variables are asked only once during the study, but the timing is conditional upon participant characteristics such as questions asked at either enrollment/screening or 1 month depending on whether the mother is a prenatal or postnatal enrollee (i.e., due date, infant DOB, single or multiple birth, child name, child sex, child ethnicity, child race); the age of the child when the mother returned to work, asked the first time postnatally the mother reports currently working for pay; or questions about timing and reasons for leaving WIC, asked when the mother indicates she no longer receives WIC.
- Other variables will be asked periodically over the course of the 24 months to capture changes over time (i.e., marital status, new pregnancy, household size, household

income, presence of infant's father, receipt of public assistance, household food insecurity, educational attainment, educational status, and employment status).

- Only a small number of variables will be asked at every post-birth interview, as current status is required for each interview (i.e., respondent still the child's caregiver; continuation/discontinuation of WIC receipt; location of WIC service receipt)

The complete list of domains and variables can be found in the Database Plan (Deliverable 10b) delivered on September 7, 2012.

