Figure: Percentage of WIC infants receiving supplemental foods using a spoon by race and ethnicity of the mother (Months 3-9)	IFPS-1 p216	Both
Figure: Percentage of WIC mothers who have used an infant feeder sometime during infancy by race and ethnicity of the mother (Cumulative, Months 3-11)	IFPS-1 p217	Both
Table: Percentage of WIC mothers who adopt supplemental food feeding practices that are generally not recommended (Cumulative; Months 1-5)	IFPS-1 p218	Both
Figure: Percentage of WIC mothers who feed supplemental foods before month 4 prior to using a spoon, by race and ethnicity of the mother (Month 3)	IFPS-1 p220	Both
Table: Self feeding skills and the percentage of toddlers who were reported to show the self feeding skill by age (Months 9, 11, 13, 18)	FITSe S53	Both
Table: Average number of months using a bottle by socio-demographics(Cumulative; months7-24)	New	Both
Feeding Practices, Working, and Childcare		
Table: Number of caregivers who work or go to school (Months 3, 7, 13, 18, 24)	New	Both
Table: Percentage distribution of children in childcare by types of childcare (Months 3, 7, 13, 24)	New	Both
Table: Average age of child when they first started childcare by type of childcare (Cumulative; Months 3, 7, 13, 24)	New	Both
Table: Frequency of barriers to breastfeeding children in childcare (Cumulative; Months 3, 7,)	New	Both
Table: Percentage of mothers with children in childcare who go to facility to breastfeed during the day (Cumulative; Months 3, 7)	New	Both
Table: Percentage distribution of who provides the food for the child by type of childcare (Months 3, 7, 13, 24)	New	Both

Table 7-2. Summary of analyses to be conducted (continued)

Table/Figure (Interview months)	Source	Sample
Feeding Practices, Working, and Childcare (continued)		
Table: Percentage of children in childcare getting human milk by age of infant and method of receipt (Months 3, 7)	New	Both
Table: Percentage distribution of accommodations available at work to assist with pumping milk (Month 3)	New	Both
Nutritional Intake		
Table: Percentage of WIC infants who receive each of the 13 groups of food at each age (Months 1-13)	IFPS-1 p225	Both
Table: Percentage of infants and toddlers consuming grains, vegetables, fruits, and meats/other protein sources, and desserts, sweets, sweetened beverages and salty snacks by age (Months 3-24)	New	Both

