Formula Supplementation	
 
■ Time until formula supplementation
 
	
 
■ Survival analysis
 
	
 
■ Socio-demographics: Age, race/ethnicity, born in US, infant first born, use of childcare, education, worked during pregnancy
 
■ Maternal and infant health: Mother's post-delivery health status, infants health status, birth weight, reported problems breastfeeding
 
■ Prenatal attitudes, beliefs and knowledge: Perceived benefits of breastfeeding, perceived barriers, how long intend to breastfeed
 
■ Prenatal experience and advice: Receipt of advice to breastfeed from physician, receipt of breastfeeding information from non-WIC sources
 
■ WIC program experience: Education, peer counseling, breast pumps, time in WIC
 

Breastfeeding cessation	
 
■ Time until cessation
 
	
 
■ Survival analysis
 
	
 
■ Socio-demographics: Age, race/ethnicity, born in US, infant first born, education, use of child care
 
■ Maternal health: Reported breastfeeding problems
 
■ Breastfeeding practices: Current use of formula
 
■ Prenatal attitudes, beliefs and knowledge: Perceived benefits of breastfeeding, perceived barriers, how long intend to breastfeed
 
■ Prenatal experience and advice: Receipt of advice to breastfeed from physician, receipt of breastfeeding information from non-WIC sources
 
■ WIC program experience: Education, peer counseling, breast pumps, time in WIC
 
■ Return to work/school: Returned to work/school within 2 months
 

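### As the plan is written, a mother's return to school is dated only if she reports paid work, so the covariate for return to work or school within 2 months cannot be determined for some student mothers

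*Combined protocol and SAP*

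**What the plan says.** Table 3-2 in Section 3.1 lists the item "Age of child when mother began school or work", with conditional checks at 3, 7, 13, 18 and 24 months. Footnote c gives the condition: "Asked the first time postnatally that the mother reports that she is currently working for pay". The bullets after the table agree with the footnote. Under the lead-in "Some variables are asked only once during the study, but the timing is conditional upon participant characteristics" they describe the item as "the age of the child when the mother returned to work, asked the first time postnatally the mother reports currently working for pay". School is not part of the trigger in either place.

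The other postnatal school item is "Current educational status", asked at the same five interviews. Employment status is asked at those interviews too. Educational attainment is asked at baseline and 24 months.

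Table 7-3 (Section 7.5) lists "Returned to work/school within 2 months" for the breastfeeding cessation model and again for the introduction-of-other-foods model. It is in italics, which the text before the table reserves for additional covariates to be explored. The second model also lists "returned to work or school" in plain type, with no time limit.

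**The concern.** The item's label covers school and work, and so does the covariate. The rule for asking the item covers paid work only. If the rule is followed, the school half of the covariate has no input for some mothers and an ambiguous input for others.

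This matters because early return is offered as a predictor of how soon breastfeeding stops and how soon cereal, fruits, vegetables and meats are introduced. A covariate that claims to include school but dates only work does not measure what its name says. The analyst would have to invent a rule for student mothers after the data are in. A start age that was not asked at the time could be recovered only by later recall.

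**Working it through.** The plan states no figure for this point, so there is nothing to reproduce. The check is to follow the written rule for each kind of mother and see whether return within 2 months can be determined. It assumes that the educational status item records whether she is currently in school.

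| Mother | Is the dating item asked? | Return within 2 months |
|---|---|---|
| Paid work only | Yes, once, at the first report of paid work | Determined |
| School only, never reports paid work | Never | No start age |
| School first, paid work later | Once, at the first report of paid work | Depends on which start is recorded; not stated |
| Neither | Never | Not returned |

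**School only.** Suppose one mother goes back to school at 5 weeks and another at 11 weeks. Two months is about 8.7 weeks, so the first should count as returned and the second should not. At the 3-month interview (about 13 weeks) both report being in school and neither is asked when it began. The status item cannot separate them. Not being in school at 3 months does nearly settle the matter, apart from a spell that began and ended before the interview.

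That partial bound needs a 3-month interview. Table 4-1 gives supplemental-sample mothers enrolled prenatally interviews at 1, 7, 13 and 24 months, so their first educational status is recorded at 7 months. Table 7-2 marks the cessation model and the tabled food-introduction models as using both samples.

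**School first, paid work later.** Suppose school starts at 5 weeks and paid work at 9 months. She first reports paid work at the 13-month interview and is asked the item then, once. If the school age is recorded she counts as returned within 2 months; if the work age is recorded she does not. The label permits either. The bullet, which speaks of returning to work, points to the second.

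**Can anything else in the plan supply the date?**

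- Imputation (Section 6.3) is for item nonresponse, and the software is described as preserving skip patterns. The plan does not say that an item skipped by design would be filled in.
- The footnote to Section 6.3 on date questions says they are repeated at each applicable interview. Under footnote c, no interview is applicable to a mother who never reports paid work.
- Table 7-2 includes age at first childcare, but starting childcare is a different event from starting school.

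**What does not need the date.** The table "Number of caregivers who work or go to school (Months 3, 7, 13, 18, 24") can be built from the status items. The plain-type covariate without a time limit can largely be built from them as well.

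**The case against.** The strongest reply is that this document does not contain the skip rule itself. Table 3-2 is offered as an example of the modular approach, the full variable list is in the Database Plan, and final instruments had already been delivered. The item's five conditional checks match both the education and the employment status rows, which would also fit a trigger on either. This stands as a limit: the finding applies to the plan as written, and the fielded question may be wider. It does not remove the conflict, because footnote and bullet both state the narrower rule.

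It can also be said that only an exploratory covariate in two models is touched, that use of child care is already a covariate in both, and that 3-month educational status gives partial information. All of this is true and limits the importance of the point. None of it makes the 2-month cut-off applicable to a student mother.

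A reader might go further and infer that school-only mothers will be coded as not returned, so that the estimated effect of early return is pulled toward the null, most of all among mothers under 20. The documents do not support that. No section says how an absent date is coded, and coding a mother as not returned when she reports school at 3 months would contradict her own answer. The documents give no share of school returners, overall or by age. The age group under 20 is a tabulation category in Appendix C; in these survival models age is a covariate, and no age-specific models are specified. Any attenuated hazard ratio would rest wholly on assumed inputs.

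**Conclusion.** The point holds for the plan as written. The dating rule conflicts with the item's own label and with the covariate in Table 7-3. Return to work or school within 2 months has no start age for school-only mothers and is ambiguous for those who start school before paid work. Educational status at 3 months bounds a school start at about 3 months and cannot place it before or after 2 months.

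The scope is one exploratory covariate in two models. The covariates carried over from the previous WIC infant feeding study and the work-or-school status table do not depend on it. The size and direction of any bias cannot be computed, because the documents give neither the number of mothers affected nor the way they would be coded. The conclusion assumes that fielding follows footnote c and the bullet; if the instrument already asks on either status, only the text needs correcting. The point is worth acting on because the remedy changes what is collected, at little cost.

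**What to change.** Check the instrument first. If it follows footnote c, change footnote c, the matching bullet and the skip rule so that the item is triggered at the first postnatal report of either school or paid work. Record the child's age at the start of each activity separately, asking the second the first time that activity is reported. Define return as the earlier of the two ages, and state this in Table 7-3. The change should be in place before the first 3-month interviews.

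The cost is at most one extra question for some mothers, since both status items are already asked at the same five interviews, plus a skip-rule change to an instrument that has been pretested and delivered.

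If the instrument cannot be changed, restrict the covariate to return to paid work within 2 months, relabel it so in both models, and specify that the age recorded is that of starting paid work. That costs nothing in the field but gives up the school component.
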